4.0 OVERVIEW OF STUDY DESIGN/INTERVENTION

4.1 Design

This study is a randomized, controlled trial to determine the efficacy of ERT-C vs. CBT-C in improving anxiety and depression symptoms, worry and rumination (primary outcomes), and caregiver and patient QOL (secondary outcomes) in distressed caregivers of/and patients with varying sites and stages of cancer (Aim 1), evaluate whether gains in emotion regulation ability and dysfunction reflect mechanisms underlying therapeutic change (Aim 2), and explore whether ERT-C is associated with reductions in biological markers of stress and inflammation (Aim 3). Participants will be 240 caregivers of patients with any site or stage of cancer who are currently receiving medical care of any kind (e.g., curative, palliative) at MSK (n=130) or MGH (n=110) who will be randomized 1:1 into ERT-C or CBT-C. We also strive to collect data from the 240 patients for whom enrolled caregivers provide care, though caregiver participation is not contingent on patient participation. 1-2 training cases per ERT interventionist will also be enrolled on this study for training purposes. Training case participants will only receive the treatment sessions and will not be asked to complete study assessments.

Potential participants will be screened for eligibility. After consenting to the study, caregiver and patient participants will complete baseline assessments (T1) (Appendix H and Appendix I). Caregivers for whom the patient does not consent to enroll are still eligible for inclusion. Caregivers will additionally provide saliva samples to measure inflammatory markers and cortisol levels (details of collection method provided below). Training case participants will not complete baseline assessments.

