Caregivers will be randomly assigned to ERT-C or CBT-C and will meet with the therapist one-on-one via telepsychiatry (e.g., Webex, Zoom, Teams) for 8 individual sessions to be completed within 8 to 16 weeks from initiation of the first session. Each session is 60 minutes in length and will be audio and video recorded (e.g. Webex, Zoom, Teams) for MSK participants. Sessions will only be audio recorded (e.g. Zoom, handheld recorders) for MGH participants. With the participant's consent, session recordings may be used for academic, educational, or training purposes. This will happen when a session is particularly compelling or represents a noteworthy example of ERT-C or CBT-C in practice. Before each treatment session (but same day as treatment session), caregivers will complete a brief assessment of emotion regulation skills (weekly measures, Appendix H). After the fourth session (mid-point of intervention), caregivers will also complete a measure of therapeutic alliance.

Within 1 week of the last ERT-C or CBT-C session, caregiver participants will complete the second assessment (T2) and saliva samples to measure inflammatory markers and cortisol levels. Additionally, caregivers will complete the third assessment and saliva samples to measure inflammatory markers and cortisol levels (T3) at 3 months (+/- 1 week) following completion of the last session, and the fourth assessment and saliva samples to measure inflammatory markers and cortisol levels (T4) at 6 months (+/- 1 week) following completion of the last session. Training case participants will not complete T2, T3, or T4 assessments.

Caregiver participants who become bereaved while on study will be given the option to withdraw or remain on study. Assessments for bereaved caregivers will not include the

Caregiver Quality of Life Index-Cancer (CQOLC) or the Caregiver Reaction Assessment (CRA). Patient participants will complete baseline assessments (T1) and at 3-months following caregiver completion of ERT-C or CBT-C (T3) (Appendix I).

Participant Reimbursement: Caregiver participants will be reimbursed for their time for participating at each timepoint (e.g. electronic gift cards, gift cards, money orders, etc). Reimbursement is structured such that each subsequent timepoint is reimbursed at a higher rate to encourage continued participation:

(T1) Baseline (T1) = \$5

(T2) Post-treatment assessment = \$10

(T3) 3-month follow-up (after ERT-C/CBT-C last session) = \$15

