(T4) 6-month follow-up (after ERT-C/CBT-C last session) = \$20

Caregiver participants will also receive \$10 at the completion of each ERT-C or CBT-C session. Caregivers who complete the entire study (i.e., all 8 sessions and all 4 timepoints) will receive \$130/participant. Patients will be compensated \$25 after the completion of their T3 assessment.

The research team will give the participant a research study receipt (Appendix J) at each timepoint.

Training case participants will not receive compensation.

Biospecimen Collection:

To evaluate inflammatory markers, caregiver participants will provide an oral mucosal transudate (OMT) sample to be collected using the OraSure collection device. MSK staff will mail MSK participants an OraSure collection device, shipping materials, collection diary (Appendix K), a copy of the slides from the instructional video (Appendix N), and a cover letter (Appendix L), MGH staff mail the same materials to participants at MGH and include an intervention-specific welcome sheet at T1 collection (Appendix MGH-H, MGH-I). The research team will email participants with an expected delivery date, a link to an instructional video, and a brief summary of the contents and description of the box. At T1 collection, the package will also include a workbook corresponding to the intervention the participant was randomized to receive (Appendix C, W).

To evaluate diurnal cortisol, caregiver participants will provide saliva samples over three days at each major timepoint. Caregivers will be instructed to swab for 2 minutes and then to remove the pad from the mouth and place it directly in the vial containing an aqueous antimicrobial preservative solution. Caregivers will collect saliva samples upon awakening, 30 minutes later, 8 hours later, and at bedtime.¹⁴⁹ Participants will be instructed to go about their normal daily activities on data collection days and will complete a diary to assess relevant health behaviors (e.g., caffeine, tobacco, and alcohol consumption; physical activity, sleep) and daily stress. To avoid sample contamination, caregivers will be instructed to avoid brushing their teeth, eating, or drinking within 20 minutes pre-sampling (Appendix K, N).

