3) *In-person recruitment*: The research team will screen daily clinic schedules (clinics listed above) to identify patients with upcoming oncology appointments. The treating clinician will either provide the caregiver directly with the contact information of the study team, or give verbal or written email permission to the study team to approach the patient-caregiver dyad at their visit. The timing of this approach will be based on the treating clinician's preference (i.e., before or after the clinic visit). When patients and caregivers are together at the clinic visit, once permission has been granted by the treating clinician to approach, the study CRC will approach both members of the dyad and describe the study. If the caregiver is interested, the CRC will verify eligibility and screen the prospective caregiver with the Distress Thermometer. If eligible, the individual will be consented to the study using the written consent. The CRC will then approach the patient to gauge interest and if interest is expressed, proceed through the screening and enrollment process. These approaches will occur in private areas (i.e. consult rooms) of the above named clinics. If the caregiver and patient prefer to think about possible participation, the CRC will let them know that s/he will follow up with them by phone/email in the next week and will proceed with a verbal consent at that time if applicable.

When a patient is at the clinic without an caregiver, the CRC will provide him/her with information about the study and ask whether the patient has a caregiver who may be interested in taking part in the study. The CRC will provide the patient with contact information for the research team and ask that the patient give this information to the caregiver who can then reach out to the team for more information. If the caregiver consents to participate, we will then ask that caregiver if they would be willing to provide the study team with the contact information of the patient for whom the caregiver provides care to screen and potentially enroll using the verbal consent process or EIC (at MGH).

Caregiver enrollment is not contingent on patient enrollment, and this will be made clear during the consent conversation with patients. It is also not necessary to enroll patients at the same time as caregivers; however, the T1 data collection for patients must occur in advance of caregivers beginning the intervention (either ERT-C or CBT-C).

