7.1 Research Participant Registration

Confirm eligibility as defined in the section entitled Inclusion/Exclusion Criteria. Obtain informed consent, by following procedures defined in section entitled Informed Consent Procedures. During the registration process registering individuals will be required to complete a protocol specific Eligibility Checklist. The individual signing the Eligibility Checklist is confirming whether the participant is eligible to enroll in the study. Study staff are responsible for ensuring that all institutional requirements necessary to enroll a participant to the study have been completed. See related Clinical Research Policy and Procedure #401 (Protocol Participant Registration).

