7.2 Randomization

Participants will be randomized upon registration in CTMS through MSKCC CRDB. Randomization will be 1:1 into ERT-C or CBT-C, stratified by site (i.e., MSK or MGH), using randomly permuted blocks of random length. MSK will provide randomization for both MSK and MGH. MSK will email MGH research staff the randomization results once they are assigned. Training case participants will get assigned to an arm (rather than randomized) based on the needs of our interventionist trainings. MGH participants will be registered in both MSK CTMS and MGH OnCore per MGH policy.

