13.2 Criteria for Study Endpoint Evaluability

Participants need to only complete the baseline assessment for the data to be considered evaluable. If any caregiver participant withdraws consent prior to baseline assessment, they will be replaced.

Caregiver outcomes include treatment-related improvements in anxiety and depression symptoms, including worry and rumination(primary outcomes) and caregiver QOL and burden (secondary outcomes).

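### Caregivers are randomized at registration and the T1 saliva kit reveals their arm, so the Aim 3 baseline is collected after disclosure and the primary-outcome baseline is not protected from it

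*Combined protocol and SAP*

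**What the plan says.** Section 7.1 sets out what registration needs: "Confirm eligibility as defined in the section entitled Inclusion/Exclusion Criteria. Obtain informed consent, by following procedures defined in section entitled Informed Consent Procedures". Completion of T1 is not listed. Section 7.2 follows: "Participants will be randomized upon registration in CTMS through MSKCC CRDB". MSK allocates for both sites and emails the result to MGH staff.

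Section 4.1, under Biospecimen Collection, describes the mailed kit: "At T1 collection, the package will also include a workbook corresponding to the intervention the participant was randomized to receive". The appendices cited there are the CBT-C manual and the ERT-C workbook forms and handouts. MGH staff also "include an intervention-specific welcome sheet at T1 collection". At T1 the caregiver gives an oral fluid sample for inflammatory markers, collects saliva for cortisol four times a day over three days, and keeps a diary of health behaviours and daily stress.

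The opening of Section 4.1 suggests another order. It places T1 after consent, adds the saliva samples, and only then says "Caregivers will be randomly assigned to ERT-C or CBT-C and will meet with the therapist one-on-one via telepsychiatry". It gives no time for the assignment. Section 16.2 has questionnaires completed in REDCap, on paper or by phone, and does not place them before or after the kit arrives.

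On early withdrawal, Section 13.2 says: "If any caregiver participant withdraws consent prior to baseline assessment, they will be replaced". Patients may enrol later than their caregiver, but Section 7.0 requires that "the T1 data collection for patients must occur in advance of caregivers beginning the intervention".

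In Section 14.0, T1 is one of the outcomes in the HADS T1–T2 model. It is the subtracted value in the change scores for worry, rumination and patient outcomes.

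**The concern.** A baseline is useful because allocation cannot have influenced it. Here caregivers know their arm for at least part of T1 and may already have read its skills material. HADS, PSWQ and RRQ are self-reports by unblinded participants. If knowing the arm changes how caregivers answer at T1, and does so differently by arm, the T1–T2 contrast measures that reaction together with the treatment effect. The Credibility and Expectancy Questionnaire is given only at T2, so no expectancy rating at baseline would help to detect this.

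Two further points follow from randomizing first. A caregiver who withdraws consent before T1 and is replaced may already have been randomized, and may have left because of the arm. A patient may be approached after the caregiver's arm is known, so agreement to take part could depend on it (Hypothesis 1b).

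**Working it through.** The plan gives no figure for this point. The check is mainly of sequence; the arithmetic shows scale under labelled assumptions.

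**1. Sequence**
- Registration requires eligibility and consent (7.1); randomization occurs at registration (7.2).
- The T1 kit holds the workbook of an arm already allocated (4.1). For T1 saliva, allocation and disclosure before baseline are therefore stated in the plan.
- The T1 questionnaires are separate from the kit (16.2). No section puts them before randomization or kit delivery, and none conceals the arm until they are done. Disclosure first is permitted, not stated.
- The order narrated at the start of 4.1 cannot hold for T1 saliva. It may hold for the questionnaires.

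**2. How a T1 shift would enter the analyses**

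Let *s* be an arm difference at T1 caused by knowing the arm.
- *Change scores (worry, rumination, patient outcomes).* Change is follow-up minus T1, so the contrast moves by the full *s*.
- *HADS, T1–T2.* Ten assessments are planned. Assume linear time, equal spacing (0 to 9, mean 4.5), complete data and a random intercept. The sum of squared deviations is 82.5, and T1's weight in the fitted T1–T2 change is 9 × 4.5 / 82.5 = 0.49. About half of *s* passes through. Non-linear time, which the plan allows, would change this weight.
- *Six-month maintenance.* This model uses T2, T3 and T4 only, so T1 does not enter.

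**3. Size for assumed shifts**

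The planning effects come from Section 14.0: d=0.50 for worry and rumination, 0.41 for depression and anxiety. Shift and effect are taken on the same SD scale.

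| Assumed *s* | Worry, rumination: *s*/0.50 | HADS: 0.49*s*/0.41 |
|---|---|---|
| 0.05 SD | 10% | 6% |
| 0.10 SD | 20% | 12% |

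For the worry and rumination test, take 240 × 0.9 / 2 = 108 per arm, two-sided alpha 0.0125, SD of change 1 and a normal approximation. The standard error is √(2/108) = 0.136.
- With no true effect, the rejection rate rises from 0.0125 to 0.019 (*s* = 0.05) or 0.040 (*s* = 0.10).
- If the shift works against ERT-C, power at d=0.50 falls from 0.88 to 0.79 or 0.67. The 0.88 is this approximation's value; the plan states 80%.

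**4. Replacement**

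If a fraction *p* of randomized caregivers withdraws consent before T1 and each is replaced until 240 have T1, then 240/(1−*p*) must be randomized. The documents give no rate for *p*.

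| Assumed *p* | Randomized | Randomized without T1 |
|---|---|---|
| 2% | 245 | 5 |
| 5% | 253 | 13 |
| 10% | 267 | 27 |

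**5. A constraint on the remedy**

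Section 14.0 (Aim 3) expects at least 75% of the 240 caregivers to give samples. Making saliva a condition of randomization could bar up to 240 × 0.25 = 60 caregivers. Section 4.1 also tells caregivers who report COVID-19 not to collect and delays collection after vaccination.

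**The case against.** The strongest reply is that no primary outcome is shown to have an unblinded baseline. The questionnaires are not in the kit, the narrative in Section 4.1 puts T1 straight after consent, and what is established concerns Aim 3, whose markers are assays rather than self-reports. This stands as a limit on the claim. It does not remove the gap: randomization at registration leaves the questionnaires free to follow disclosure, and the diary kept alongside the saliva samples is a self-report.

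A second reply is that both arms are active therapies, matched in number, frequency and duration of sessions and each with a workbook, so there is little reason to expect a differential shift. Nothing in the documents shows one. The 0.05–0.10 SD is an assumption, and its direction is unknown.

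A third is that Section 13.2 is an accrual rule. It covers withdrawal of consent only, and replacement in itself biases nothing. That is fair. People who withdraw consent before T1 leave no data under any rule. This favours randomizing later, because they would then not be part of the randomized group.

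On patients, Sections 7.0 and 14.0 show that later enrolment is allowed and that at least 50% participation is anticipated. They do not show that patients are usually approached after the arm is known. Section 7.0 also describes approaching both members of the dyad at one visit. Selection by arm is a possibility only.

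**Conclusion.** The point holds in this form. The Aim 3 baseline (T1 saliva and diary) is collected after the arm is revealed and with treatment material in hand. For HADS, PSWQ and RRQ the plan permits the same without stating it, and Sections 4.1 and 7.2 need to be reconciled. A differential T1 shift would carry over fully into the worry, rumination and patient change scores and about half into the HADS T1–T2 contrast under the linear, equally spaced, complete-data assumption. An assumed 0.05–0.10 SD is 10–20% of d=0.50 for worry and rumination and 6–12% of 0.41 for HADS. Some caregivers replaced under Section 13.2 may already have been randomized; their number is unknown.

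A reader might infer more: that every primary outcome has an open-label baseline, that T1 enters all efficacy analyses, or that all randomized caregivers who leave early are dropped. The documents do not support these readings. Questionnaire timing is not stated, the maintenance model excludes T1, and Section 13.2 concerns consent withdrawn before baseline.

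**What to change.** - **Section 7.2:** randomize only after the caregiver's T1 questionnaires are complete, and the patient's as well if the patient has agreed to take part by then. Do not make saliva a condition of randomization.
- **Section 4.1:** take the workbook and welcome sheet out of the T1 kit. Send them by email or a second mailing once T1 saliva is collected or its collection window has closed, and before session 1. Align the opening narrative with Section 7.2.
- **Section 13.2:** limit replacement to withdrawals before randomization. Count and report every randomized caregiver and keep each in the assigned arm.
- **Caregivers already enrolled:** use T1 completion and kit-dispatch dates to flag T1 data collected after disclosure, and run a sensitivity analysis on that flag.

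The cost is a short amendment, one extra email or mailing per caregiver, and a short delay before session 1. The meditation recordings are already sent by email.

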Caregivers will be instructed to keep samples in the freezer prior to returning them to the research laboratory and to ship samples as soon as possible after the last collection day. The samples and the collection diary should be shipped using the shipping materials and return label provided to:

[name]
Program in Public Health
[name]
[name]
[name]

Samples will be shipped by secured mail and are stable at standard temperatures for up to 21 days from collection. At-Home Saliva collection distribution and mailing details are included in Appendix M.

If a participant reports receiving the COVID-19 vaccine while on study, the study team will document the date of vaccination receipt. If the date of vaccination fall within 7 days of a biospecimen collection timepoint window, the participant will be instructed to not collect any samples until 7 days have passed since their vaccination. If a participant reports a COVID-19 diagnosis at any collection point, the study team will document this and instruct them not to collect biospecimens.

Training case participants will not provide biospecimen collection.

Consultant and Collaborator Roles

The research team will be led by Drs. [name] and [name] and brings together research leaders in Emotion Regulation Therapy (Drs. [name], [name], and [name]), Cognitive Behavioral Therapy (Drs. [name] and [name]), psychoneuroimmunologic correlates of distress ([name]), and biostatistics ([name]). Study implementation will also rely on support roles including a Clinical Research Coordinator and Clinical Research Supervisor.

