6.2 Participant Exclusion Criteria

Caregivers

- 1) As per self-report, presence of disorder that compromises comprehension of assessments or informed consent information (e.g., dementia).
- 2) As per the judgement of the consenting professional, clinical, PI, and/or as per the medical record, severe psychopathology or cognitive impairment which is likely to interfere with the participation or completion of the protocol or their ability to provide meaningful information.
- 3) As per self-report, currently engaged in regular individual psychotherapeutic support (that the participant is unable or unwilling to put on hold for the course of treatment).
- 4) As per self-report, a lifetime history of bipolar disorder, schizophrenia, or schizoaffective disorder.
- 5) As per self-report, has medical condition or medication use known to confound measures of systemic inflammation (e.g., autoimmune disorder, inflammatory disease; uncontrolled thyroid disease; active infection; myocardial infarction or stroke in the last 6 months; Type I diabetes; acute hepatitis; vaccination in the last 7 days for viral disease). (N/A for training case participants)
- 6) As per self-report, is a regular smoker, defined as having more than 2 cigarettes per day on most days. (N/A for training case participants)
- 7) As per self-report, providing care for a patient who has a caregiver currently or formerly enrolled in this study (‘formerly enrolled’ is N/A for training case participants).
- 8) As per self-report, currently enrolled in another study focused on supportive care for caregivers (MGH participants only).

Patients

- 1) Presence of disorder that compromises comprehension of assessments or informed consent information (e.g., dementia) as per EMR or clinician judgment.
- 2) As per the judgement of the consenting professional, clinical, PI, and/or as per the medical record, severe psychopathology or cognitive impairment which is likely to interfere with the participation or completion of the protocol or their ability to provide meaningful information

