11.0 EVALUATION DURING TREATMENT/INTERVENTION

MEASURE/TEST	Time to complete	Intervention Sessions (ERT-C or CBT-C) ^a	T2 (1-wk post last ERT-C or CBT-C) ^{b, e}	T3 (3-mos post ERT-C or CBT-C) ^e		T4 (6-mos post ERT-C or CBT-C) ^e
				Caregiver	Pt	
		Caregiver Only	Caregiver Only	Caregiver	Pt	Caregiver Only
Distress Thermometer (DT)	2 min	X	X	X		X
Hospital Anxiety and Depression Scale (HADS)	5 min	X	X	X		X
Penn State Worry Questionnaire (PSWQ)	5 min		X	X		X
Rumination-Reflection Questionnaire, Rumination subscale (RRQ-R)	5 min		X	X		X
Attentional Control Scale (ACS)	5 min	X	X	X		X
Experiences Questionnaire, Decentering subscale (EQ-D)	5 min	X	X	X		X
Emotion Regulation Questionnaire, Reappraisal subscale (ERQ-R)	3 min	X	X	X		X

Caregiver Quality of Life Index-Cancer (CQOLC) ^f	5 min		X	X		X
Caregiver Reaction Assessment (CRA) ^f	5 min		X	X		X
Self-Administered Comorbidity Questionnaire (SCQ)	5 min		X	X		X
Patient-Reported Outcomes Measurement Information System Global Health Scale (PROMIS-GH)	4 min		X	X	X	X
Credibility and Expectancy Questionnaire (CEQ)	2 min		X			
EORTC QLQ-C30	3 min				X	
Perceived Stress Scale (PSS)	4 min				X	
National Survey on Drug Use and Health (NSDUH), Healthcare Utilization	2 min				X	
Working Alliance Inventory-Short Form (WAI-SF)	8 min	X ^c				
COPE, Active Coping Subscale	2 min.	X				
Inflammatory Markers Assessment	5 min		X	X		X
Diurnal Cortisol Assessment	2 min. 4x a day over 3 days		X ^d	X		X
Total Time		22 min	80 min	78 min	13 min	78 min

^a ERT-C or CBT-C will be delivered over 8 individual sessions by a trained study therapist. The 8 sessions must be completed within 8 to 16 weeks from initiation of the first session. ^b Questionnaires at T2 should be completed on the same day as the last session, but may be completed within 1 week. ^c The Working Alliance Inventory will be administered after the fourth intervention session. ^d Saliva collection at T2 should begin the day after the last session. ^e Training case participants will not be asked to complete follow-up assessments. ^f Bereaved caregivers who report their loved one passing away will not be asked to complete these assessments.

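### Any active infection or recent viral vaccination bars entry as a confounder of the inflammation markers, but the visible rules at sample collection cover only COVID-19

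*Combined protocol and SAP*

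**What the plan says.** Section 6.2, caregiver exclusion 5, removes anyone who by self-report "has medical condition or medication use known to confound measures of systemic inflammation". Its examples include "active infection; myocardial infarction or stroke in the last 6 months; Type I diabetes; acute hepatitis; vaccination in the last 7 days for viral disease". Neither the infection nor the vaccination item is limited to COVID-19.

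Section 4.1 (Biospecimen Collection) gives the rules that apply once a caregiver is on study. For vaccination: "If a participant reports receiving the COVID-19 vaccine while on study, the study team will document the date of vaccination receipt". If that date is within 7 days of a collection window, "the participant will be instructed to not collect any samples until 7 days have passed since their vaccination". For illness: "If a participant reports a COVID-19 diagnosis at any collection point, the study team will document this and instruct them not to collect biospecimens".

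Timing at T2 is set in two places. Section 4.1 says "Within 1 week of the last ERT-C or CBT-C session, caregiver participants will complete the second assessment (T2) and saliva samples", and footnote d to the Section 11.0 table says "Saliva collection at T2 should begin the day after the last session". T3 and T4 each allow one week either side of the target date. Cortisol is collected four times a day over three days. The inflammatory markers come from an oral mucosal transudate (OMT) sample, for which no multi-day schedule is stated.

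Section 14.0 (Aim 3) names no covariate, exclusion or sensitivity analysis for infection or vaccination.

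**The concern.** The protocol has already judged which short-lived states distort IL-6, CRP and sTNF-alpha-RII, and it applies that judgement when caregivers enter rather than when the markers are measured. A caregiver with an influenza vaccination two days earlier, or a current respiratory infection, would be turned away at screening but would sample as normal at T2, T3 or T4. T1 is exposed too: the T1 kit is mailed with the workbook for the randomized arm, so that sample also follows the eligibility check.

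Two further gaps concern COVID-19 itself. Vaccination leads to a delay, but a diagnosis leads only to an instruction not to collect, and staff at two sites are not told whether collection resumes. Nor does the text say whether a deferred sample may fall outside its window, which matters most at T2. At stake are the precision and completeness of the biomarker data for Hypothesis 3a.

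**Working it through.** **Coverage, side by side (visible text)**

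| State | At entry (6.2, item 5) | At T1–T4 collection (4.1) |
|---|---|---|
| COVID-19 vaccine, last 7 days | excluded | deferred |
| Other viral vaccine, last 7 days | excluded | no rule |
| COVID-19 | excluded if active infection | do not collect; later collection not addressed |
| Other active infection | excluded | no rule |

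The diary examples in Section 4.1 (caffeine, tobacco, alcohol, activity, sleep, daily stress) name neither infection nor vaccination. The comorbidity questionnaire repeated at follow-up covers 12 defined medical problems and 3 optional conditions.

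**T2 window.** Let day 0 be the last session, with samples due by day +7 and planned to start on day +1. For vaccination on day v, the earliest start is v+7 and a three-day series ends on v+9.

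| v | Earliest start (OMT possible) | Cortisol ends | Within one week? |
|---|---|---|---|
| −5 | 2 | 4 | yes |
| −4 | 3 | 5 | yes |
| −3 | 4 | 6 | yes |
| −2 | 5 | 7 | yes |
| −1 | 6 | 8 | OMT yes, cortisol no |
| 0 | 7 | 9 | OMT yes, cortisol no |

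All six cases miss the day-after-session start. If the 7-day wait is read strictly, so that sampling starts at v+8, the cortisol series overruns for v = −2, −1 and 0, and for v = 0 the OMT sample also slips to day 8.

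**T3 and T4 windows.** Each runs from day −7 to day +7 around the target.
- Start planned on the target date: vaccination on days −6 to −2 still fits, and only day −1 overruns (series ends on day +8). With a start at v+8, days −2 and −1 overrun.
- Start planned at the opening of the window: every deferral fits.
- Start planned for the last feasible day (+5): every deferral overruns.

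**Aim 3 sample size.** The plan's analytic number reproduces: 240 × 0.75 × 0.80 = 144. Its power statement does not. With 72 per arm and d = 0.36, a two-sample t-test at two-sided 0.05 (assumed, as Aim 3 states no alpha) has about 57% power, and 80% power needs d = 0.47. That is a separate matter and this point does not rest on it, but it shows there is little slack.

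**Noise from affected samples.** Assume a fraction p of collections is affected, each shifted by δ, measured in SDs of the analysed outcome. Variance is multiplied by 1 + p(1−p)δ².
- p = 0.03, δ = 0.5: 1 + 0.0291 × 0.25 = 1.007, equivalent to 144/1.007 ≈ 143 caregivers.
- p = 0.05, δ = 1: 1 + 0.0475 × 1 = 1.048, equivalent to 144/1.048 ≈ 137.
- p = 0.10, δ = 1.5: 1 + 0.09 × 2.25 = 1.203, equivalent to 144/1.203 ≈ 120.

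Neither p nor δ is in the documents.

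**Missing samples.** If collection does not resume after a COVID-19 diagnosis, that timepoint loses the OMT sample and 4 × 3 = 12 cortisol samples. No rate is given. If a further 2%, 5%, 10% or 15% of the 144 were lost entirely, n would be about 141, 137, 130 or 122, and the effect detectable with 80% power would be d ≈ 0.475, 0.483, 0.496 or 0.511, against 0.470 at n = 144.

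**The case against.** The strongest reply is that this is a small matter in a part of the trial that the protocol summary describes as exploring biomarkers. The primary outcomes are questionnaires and are untouched. The sampling rule is the same in both arms, so what is shown is extra noise rather than bias between arms. The mixed model keeps caregivers who miss a timepoint, so one missed collection does not remove a caregiver and the loss figures above lean high. The variance range is assumed, and its low end is negligible. All of this stands, and it limits the weight of the point.

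Four stronger readings are tempting, and the documents do not support them.
- A reader might infer that the deferral collides with the T3 window. A 15-day window absorbs most deferrals, and T4 has the same width.
- A reader might infer that anyone vaccinated from the day before the last session onward cannot finish T2 on time. A series started on day +1 ends on day +3, so vaccination on days 4 to 7 comes after it is complete. On the v+7 count, the OMT sample also stays inside the week.
- A reader might infer that samples after a COVID-19 diagnosis are discarded for good. The text says not to collect and is silent on later collection. T1 has no numeric window that would prevent a delay.
- A reader might infer that affected samples can never be identified. The diary list is introduced as examples, and Appendices K, M and N, which hold the log, instructions and slides, are not in the reviewed text.

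What the reply does not remove is the mismatch between exclusion 5 and the sampling rules, or the lack of any stated flag in Aim 3.

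**Conclusion.** The point holds as a cheap improvement, with medium confidence. On the visible text, the protocol's own confounders of systemic inflammation are screened at entry but, apart from COVID-19, not at any of the four collections. The COVID-19 rules leave open whether collection resumes after a diagnosis and whether deferred samples may fall outside their window. The T2 conflict is confined to the day-after start, for every deferral, and to the cortisol series, for vaccination on day −1 or 0 (day −2 as well on the stricter count).

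The consequence is added noise and some avoidable missing samples in Aim 3. Its size is not known from the documents: under the stated assumptions variance rises by about 1% to 20%, and the upper figure needs both extreme inputs together. The conclusion assumes that the unseen appendices do not already ask about infection and other vaccines.

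**What to change.** 1. Reconcile the COVID-19 paragraph in Section 4.1 with exclusion 5, so that the same confounders are asked about before each collection from T1 to T4. Two yes/no items with dates in the collection diary are enough, if Appendix K does not already have them.
2. State one consistent deferral rule, set by the sponsor, for vaccinations and for infections including COVID-19, and say explicitly whether collection resumes after a diagnosis.
3. Allow a bounded, biospecimen-only extension of the windows for deferred samples, and align it with footnote d in Section 11.0. A deferred T1 sample must still precede the first session, since Section 14.0 treats T1 as pre-intervention.
4. Add to Section 14.0, Aim 3, a prespecified sensitivity analysis that omits flagged samples.

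The cost is two diary items, one revised paragraph in Section 4.1 with matching text in Appendix M, and one sentence in the analysis plan. The downside is that a few samples will be collected later than the questionnaires they accompany; the bound on the extension limits that gap.
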